3.2.4 Unplanned endpoints

Following unblinding of the trial data, the following unplanned endpoints, published since the inception of the trial, were added to the trial report:

- PASDAS very low disease activity (PASDAS<1.9; Y/N) at 12, 24, 36 & 52 weeks
- PASDAS moderate or good response (Y/N) at 12, 24, 36 & 52 weeks
- PASDAS meaningful change value for improvement achieved (Y/N) at 12, 24, 36 & 52 weeks

3.3 Study variables

3.3.1 Standard variables

- Age
- Sex
- Ethnicity
- Height
- Weight
- Medical / surgical / family history
- Concomitant medication

3.3.2 Efficacy variables

- PASDAS (0-10)
- Leeds Enthesitis Index (0-6)
- Physician assessment of arthritis, Likert scale (1-5; used in composite outcomes)
- Physician global assessment of psoriatic disease VAS (mm; used in composite outcomes)
- Leeds Dactylitis Index (0-~40)
- Psoriasis Area Severity Index (0-72)
- Modified Nail Psoriasis Severity Index (0-140)
- Tender joint count (out of 68; used in composite outcomes)
- Swollen joint count (out of 66; used in composite outcomes)
- Composite Psoriatic Disease Activity Index (range 0-15)

- Minimal disease activity (yes/no)
- PsARC response (yes/no)
- ACR response (yes/no)
- Percentage of Body Surface Area (%)
- C-reactive protein level (mg/L; used in composite outcomes)
- US grey scale score (total 0-72; 0-144 for OMERACT definition subset)
- US power Doppler score (total 0-72; 0-144 for OMERACT definition subset)
- US GLOESS score (total 0-72; 0-144 for OMERACT definition subset)
- US number of entheses with grey scale abnormalities (0-10; 0-12 for OMERACT definition subset)
- US enthesis power Doppler score (total 0-30; 0-36 for OMERACT definition subset)
- US total enthesis thickness score (0-30; 0-36 for OMERACT definition subset)
- US total enthesis erosion score (0-30; 0-36 for OMERACT definition subset)
- US number of entheses with calcification (0-10)
- US number of entheses with enthesophytes (0-10)
- US enthesis inflammation score (0-70)
- US enthesis chronicity score (0-50)
- US remission (yes/no)
- Patient assessment of arthritis, Likert scale (1-5; used in composite outcomes)
- Patient global assessment of psoriatic disease activity VAS (mm)
- Patient articular pain assessment VAS (mm; used in composite outcomes)
- ASQoL (0-18; used in composite outcomes)
- Health Assessment Questionnaire Disability Index (0-3; used in composite outcomes)
- Dermatology Life Quality Index (0-30)
- SF-36 mental and physical component scores (0-100)
- Cumulative dose of steroid (mg)
- SPARCC spinal inflammation score (0-108)
- SPARCC sacro-iliac joint inflammation score (0-72)
- HIMRISS BML score (0-100)
- HIMRISS effusion & synovitis score (0-30)
- KIMRISS score (0-763)
- CANDEN spine inflammation score (0-614)
- CANDEN spine fat score (0-510)

- CANDEN spine bone erosion score (0-208)
- CANDEN new bone formation score (0-460)
- HEMRIS score (inflammation sum score 0-24; structural sum score 0-18)
- MRI-WIPE score (0-738)
- T-cell subset frequencies (IRC, naïve, Treg)
- B-cells

3.3.3 Safety variables

- Number of patients experiencing SAEs and AEs.
- Any clinically significant worsening of a pre-existing condition.
- An AE occurring from overdose of an IMP, whether accidental or intentional.
- An AE occurring from abuse (e.g. use for nonclinical reasons) of an IMP.
- An AE that has been associated with the discontinuation of the use of an IMP.

4. STUDY METHODS

4.1 Overall Study Design and Plan

GOLMEPsA is an investigator initiated, randomised, double-blind, placebo-controlled, two-armed, parallel-group, single-centre imaging-aided study. Patients with the following criteria will be recruited:

[figure not shown]
- Treatment-naïve PsA patients classified according to CASPAR criteria^[12]
- <24 month diagnosis
- At least 3 swollen and 3 tender joints or 2 swollen and 2 tender joints and one tender enthesis.

The trial will start with a four-week screening phase, and informed consent will be obtained at the screening visit. A total of 84 patients will be randomised on a 1:1 basis to receive one of the following:

Treatment Arm 1 (Group A): Immediate golimumab (50 mg SC four weekly) and MTX (starting at 15 mg weekly with rapid escalation up to 25 mg over 4 weeks) combination therapy administered for a total duration of 24 weeks.

Treatment Arm 2 (Group B): MTX monotherapy (starting at 15 mg weekly with rapid escalation up to 25 mg over 4 weeks) plus placebo SC injections four weekly for 24 weeks.

Both treatment arms will receive a “bolus” dose of methylprednisolone (120mg IM or equivalent amount intra-articularly in case of oligoarticular, ≤4 swollen joints, presentation) with the aim to achieve rapid ablation of inflammation at baseline. In addition, both treatment arms will adopt a “treat-to-target” (TT) algorithm (see Schematic Diagram) involving further corticosteroid injections (intra-muscular or intra-articular) if not achieving a PsARC response at weeks 8 and 12 (secondary endpoint). Steroid amount given between both visits will not exceed a maximum amount of 120mg methylprednisolone per patient.

4.2 Selection of Study Population

Key inclusion criteria (pertinent to primary endpoint)

- Subjects with a diagnosis of psoriatic arthritis as per the Classification for Psoriatic Arthritis (CASPAR) criteria confirmed up to 24 months prior to screening.
- Subjects with active PsA defined as the presence of at least 3/78 tender and at least 3/76 swollen joints or 2 swollen and 2 tender joints plus one affected enthesal site (Achilles tendon and/or plantar fascia) at baseline.

Key exclusion criteria (pertinent to primary endpoint)

- Previous treatment with any conventional or biological DMARDs, where “treatment” is defined as a therapeutic dosage according to each product’s SmPC. Topical preparations for psoriasis are not considered DMARDs (examples include, but are not limited to, steroids, salicylic acid, tar).
- Any chronic inflammatory arthritis diagnosed before 16 years old.

- Patients who have received any systemic/intra-articular corticosteroids within 4 weeks prior to screening. Topical preparations with steroids for cutaneous use, or inhalers for the treatment of asthma are not considered systemic/intra-articular corticosteroids.

4.3 Method of Treatment Assignment and Randomization

Patients will be randomised on a 1:1 basis to receive combination therapy of golimumab and methotrexate or methotrexate monotherapy and placebo. Randomly-permuted block sizes will be used; randomisation will be stratified by the number of involved joints at baseline (oligoarticular: ≤ 4 joints involved /polyarticular: >4 joints involved). Informed written consent for entry into the trial must be obtained prior to randomisation, subject to the patient meeting the eligibility criteria. Randomization should take place as soon as possible after consent is obtained and must be performed by an authorized member of the clinical team at the site using the LTHT Pharmacy telephone randomisation service.

4.4 Treatment Masking (Blinding)

Pre-filled syringes will be available from pharmacy (provided by Janssen Biologics) with identical external appearance and no identifiers aside from the patient's study number. The internal fluid will be visible to the naked eye. It will be impossible for either the patient or the study nurse/doctor to identify the product as either golimumab or placebo. This will be provided by Janssen Biologics and will consist of an aqueous medium of histidine sorbitol and polysorbate 80 at pH 5.5.

5. SEQUENCE OF PLANNED ANALYSES

5.1 *Interim Analyses*

There are no planned Interim Analyses for this study.

5.2 *Final Analyses and Reporting*

All final, planned, analyses identified in the protocol and in this SAP will be performed only after the last patient has completed the week 52 visit, with the exception of baseline analyses (see below). A blinded data review meeting will be held prior to database lock and completion of the final analyses.

In addition, no database may be locked, random code unblinded, or analyses completed until this SAP has been approved.

Key statistics and study results will be made available to the study team following database lock and prior to completion of the final CTR.

Analyses using either screening and baseline data (PASDAS test-retest reliability) or baseline data only (associations between clinical and imaging assessments at baseline) will be performed as soon as all the relevant patients have completed these visits and the relevant data have been fully validated and locked to further amendment. In the case of MRI, no analyses of the baseline data will be performed until all patients in the subset in whom MRI measurements were obtained at baseline have completed the follow-up MRI visits, and all MRI data have been fully validated, because MRI data from all visits will be scored simultaneously. As these analyses do not involve post-treatment efficacy comparisons and can be performed blind to treatment group there will be no impact on multiplicity and no potential to unblind the trial.

Any, post-hoc, exploratory analyses completed to support planned study analyses, which were not identified in this SAP, will be documented and reported in appendices to the CTR. Any results from these unplanned analyses will also be clearly identified in the text of the CTR.

Analysis of exploratory WB-MRI outcomes may be conducted after the primary and secondary outcomes have been analysed and reported; in which case this analysis will be attached as an addendum to the main CTR.

6. SAMPLE SIZE DETERMINATION

Using in-house unpublished data we estimated the minimum clinically important difference to be 0.7 units on the PASDAS; this is similar to a published value for smallest detectable difference of 0.8 units^[13]. We will aim to detect a difference of at least 1 unit between the treatment arms in this study. The standard deviation of PASDAS in the TICOPA MTX rapid escalation arm^[14,15] at 24 weeks (restricted to patients who remained on methotrexate throughout) was 1.57. Assuming $\delta=1$, $\sigma=1.57$, at $\alpha=0.05$ and $1-\beta=0.8$ this would require 78 patients. Originally the sample size for the trial was adjusted to account for 10% drop-out, requiring a total of 88 (44 per group). However, because recruitment had been slower than anticipated, in part due to the SARS-CoV-2 pandemic, drop-out was reassessed once 76 participants had the opportunity to reach the primary endpoint. Only 4 (5%) had withdrawn from follow-up prior to that point. Therefore, the total required sample size was revised down to 84 (42 per group) i.e. allowing for 5% drop-out.

For the whole-body MRI subset, published rules of thumb for pilot studies indicate that between 12 and 30 patients per group should be included. We will aim to continue recruiting patients into the WBMRI subset until there are at least 30 patients (15 per group) with scans available at both baseline and week 24, at which point WB-MRI will cease to be performed in the remaining patients.

To estimate the ICC between two repeated readings of the PASDAS composite index with a confidence interval of width 0.2, we would need 31 patients assuming the ICC is 0.85. For the patient's global assessment of disease activity VAS, which provides the greatest loading on the PASDAS score, $ICC = 0.87^{[1]}$. This element was added in an amendment and will not be available for all patients; we will aim to obtain data from at least 31 patients.

7. ANALYSIS POPULATIONS

The following analysis populations are planned for the study:

- **Screening Population (SCREEN):** The Screening Population includes all subjects who provide informed consent and provide demographic and/or baseline screening assessments, regardless of the subject's randomization and treatment status in the trial.
- **Safety Population (SAFETY):** The Safety Population includes all patients who receive any amount of planned study medication.
- **Full Analysis Set (EFFICACY):** The Efficacy Population includes all patients who are randomized.
- **Per-Protocol Efficacy (PP-EFFICACY):** The PP-Efficacy includes all patients in the Efficacy Population deemed to fulfil the protocol in terms of eligibility, interventions and outcome assessment (see section 9.2).

8. GENERAL ISSUES FOR STATISTICAL ANALYSIS

8.1 Analysis Software

All analysis will be performed using Stata software version 17.0.

8.2 Methods for Withdrawals, Missing Data, and Outliers

For missing values at baseline, screening values (if available) will be carried forward.

Visits which fall outside ± 14 days of the scheduled date will be considered missing for analysis.

For patients who withdraw early, in the primary analysis data from the withdrawal visit will be imputed for subsequent visits for continuous outcomes, and non-response will be imputed for binary outcomes.

Multiple imputation by chained equations will be used to address the remainder of the missing data for primary and secondary outcomes. The number of imputed datasets will be determined by the Monte Carlo (MC) error rate of the resulting combined estimates. A minimum of 20 datasets will be imputed; if the MC errors calculated for the coefficient and standard error for the treatment group term are more than 10% of the estimated standard error the number of imputations will be increased in increments of 5 until the MC error is <10% of the standard error. Continuous interval, count or ordinal outcomes will be imputed using predictive mean matching to 10 nearest neighbours; categorical outcomes will be imputed using binary, ordinal or multinomial logistic regression as appropriate to the data type. Composite measures, including the primary outcome, and the achievement of thresholds of response (e.g. PsARC) will be computed passively following imputation of the underlying score or components, provided sample size is sufficient for the imputation models to converge. If the number of parameters to be estimated exceeds the number of patients, these variables will be directly imputed.

All imputation models will include:

Age at baseline, sex, oligo/polyarticular disease, treatment arm, symptom duration at baseline, baseline values of the variables being imputed (values of components for response variables), other auxiliary variables found to be associated with the outcome to be imputed and/or with the likelihood that it is missing. Only values from the main primary and secondary endpoints (12, 24, 36, 52 weeks) will be included in imputation models. If imputation models continue to fail, mixed modelling will be explored as an alternative – see section 11.2 for details.

Sensitivity analyses relating to missing data will include restricting analysis of the data to the observed values only (1), and using post-treatment-withdrawal data observed for patients who withdrew from study therapy early (where available) rather than carrying forward data from their withdrawal visit (2).

Outliers, defined as values lying more than 3 times the inter-quartile range from the nearest quartile, will be identified during the blind data review. Those that can be confirmed to be due to data entry errors will be corrected in the database. In all other cases outliers will be included in the main analysis but sensitivity analyses will be performed to assess whether the exclusion of these data points affects study conclusions. The same approach will be used for cases identified to be unduly influential during the analysis of continuous outcomes; for example cases for which the studentized residuals from the linear regression model exceed an absolute value of 2.5.

Analysis of exploratory WB-MRI outcomes will be available case only.

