3.2.2 Secondary Endpoint(s)

Secondary endpoints are:

Efficacy measures

Clinical measures of disease activity

- Disease activity measures:
 - PASDAS at 12, 36 and 52 weeks
 - Enthesitis score⁽²⁾ at 12, 24, 36 and 52 weeks
 - Dactylitis score^(3,4) at 12, 24, 36 and 52 weeks in patients with dactylitis
 - PASI score^[5] at 12, 24, 36 and 52 weeks
 - mNAPSI score^[6] at 12, 24, 36 and 52 weeks
 - CPDAI score^[7] at 24 and 52 weeks
- Acceptable state or response:
 - Proportion achieving MDA at 12, 24, 36 and 52 weeks
 - Proportion achieving PsARC response at 8, 12, 24, 36 and 52 weeks
 - Proportions achieving ACR20/50/70 responses at 12, 24, 36 and 52 weeks
 - Proportion achieving at least PASI75 at 12, 24, 36 and 52 weeks in the subset of patients in whom at least 3% of the BSA was affected by psoriasis at baseline
- Composite index test-retest reliability
 - PASDAS score at screening and at baseline visit

Imaging measures of disease activity

- Measures of joint/enthesis pathology
 - Total scores for synovitis/enthesis identified by US at 12, 24 and 36 weeks
 - GLOESS score^(8,9)
 - Inflammatory enthesitis score
 - Chronic enthesitis score
- Acceptable state
 - Proportion achieving US remission (all common joints and entheses (see section 8.7) score GS<2 & PD==0) at 12, 24 and 36 weeks

Patient-reported outcomes

- Patient VAS global disease activity at 24 and 52 weeks
- Quality of life
 - DLQI score^[10] at 24 and 52 weeks
- Health status
 - SF-36 mental component summary and physical component summary^[11] at 24 and 52 weeks.

Other secondary endpoints

- Treatment-related endpoints
 - Proportion of patients requiring additional steroid therapy up to week 12
 - Cumulative steroid dose received up to week 12*

*This was originally planned; however, inspection of blinded data indicates that all participants who received additional steroid received one IM dose of 120mg, therefore this analysis will not be performed as this is already captured in the proportion requiring additional steroid therapy

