11.2 Secondary Efficacy Variable Analysis

Full descriptive data will be provided for all secondary endpoints. Adjusted estimates of effect size will be provided for binary secondary endpoints using multiple binary logistic regression; odds ratios and 95% confidence intervals will be presented. This applies to MDA, PsARC response, ACR 20/50/70, PASI75, US remission, steroid therapy required up to week 12 (Y/N). Continuous interval outcomes will be analysed using multiple linear regression; differences between treatment group means and 95% confidence intervals will be presented. This applies to PASDAS, CPDAI, patient global VAS, SF36 PCS and MCS, US outcomes. Count outcomes will be analysed using an appropriate generalised linear model (see Table 11.2.1); incident rate ratios and 95% confidence intervals will be

presented. If negative binomial regression is used, the mean dispersion parameter will be applied. In the case of missing scores for individual joints, the exposure will be amended to indicate the number of joints/enthuses assessed. This applies to the Leeds enthesitis index, the Leeds dactylitis index, & mNAPSI. Severely skewed outcomes for which an appropriate generalised linear model cannot be identified will be analysed using quantile (median) regression; differences between medians and 95% confidence intervals will be presented. If the median is 0 in both groups then alternative point of comparison will be attempted in the following sequence until model convergence is achieved: 75th percentile, 90th percentile, 95th percentile. This applies to PASI & DLQI. All analyses will control for the stratification factor and baseline values of the outcome where relevant. Two-sided significance at $p<0.05$ will be the criterion applied to all secondary outcomes. If a statistically significant difference is not found for the primary outcome, all secondary outcomes will be considered exploratory.

Table 11.2.1: Models to be used for analysis of secondary outcomes

The appropriateness of these models has been determined following initial blind review of the data. In the event that, once allocation is known, the specified model fails to converge, an alternative model will be used and this deviation from the SAP will be highlighted in the trial report

Outcome(s)	Model
LEI	Negative binomial
LDI	Negative binomial
PASI	Quantile (median) regression
mNAPSI	Negative binomial
DLQI	Quantile (median) regression

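### The 3 × IQR outlier fence in SAP 8.2 has no rule for an IQR of 0, so for zero-heavy secondary scores the outlier-exclusion sensitivity analysis can be left with nothing but zeros

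*SAP*

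**What the plan says.** SAP 8.2 gives a single definition, "Outliers, defined as values lying more than 3 times the inter-quartile range from the nearest quartile", and says that such values "will be identified during the blind data review". Confirmed data-entry errors are corrected. For the rest, "In all other cases outliers will be included in the main analysis", and "sensitivity analyses will be performed to assess whether the exclusion of these data points affects study conclusions". The definition names no outcome type and makes no provision for an IQR of 0. The companion rule in the same paragraph, on large studentised residuals, is tied to continuous outcomes; the IQR rule is not.

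SAP 11.2 describes the scores that matter here. On count models it says: "This applies to the Leeds enthesitis index, the Leeds dactylitis index, & mNAPSI"; Table 11.2.1 assigns all three to negative binomial regression. PASI and DLQI go to quantile regression, with this fallback: "If the median is 0 in both groups then alternative point of comparison will be attempted", moving in turn to the "75th percentile, 90th percentile, 95th percentile". SAP 3.2.2 lists the dactylitis score "at 12, 24, 36 and 52 weeks in patients with dactylitis", without saying when a patient must have dactylitis to count. Protocol 3.2 lists the same endpoint without that restriction.

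**The concern.** A quartile-based fence assumes that the middle half of the data has some spread. A score with a floor at 0 may have none, because after treatment many patients can sit at 0. If the upper quartile is 0, so is the IQR, and a positive score of any size lies beyond the fence. The rule then picks out residual enthesitis, dactylitis, nail or skin disease instead of rare or implausible values, and residual disease is what the two arms are being compared on.

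At stake is the usefulness of a stated robustness check. The plan intends it to show whether a few extreme values drive a conclusion. For a zero-heavy score it cannot show that, because it removes either all or a large part of the information on treatment effect.

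**Working it through.** **Setting.** The number randomised is 84, 1:1 (SAP 4.1 and 6). The plan's figure reproduces: 2 × (1.96 + 0.84)² × 1.57² / 1² ≈ 38.7, so 39 per arm and 78 in total; 78 / 0.95 = 82.1, so 83, or 84 for equal arms. The software is Stata 17.0 (SAP 8.1), so quartiles follow Stata's default percentile definition. Quartiles are taken as pooled over arms at one visit. The SAP does not say this, but a blind review implies pooling.

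**Rule.** Flag x if x < Q1 − 3(Q3 − Q1) or x > Q3 + 3(Q3 − Q1).

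**Where it collapses.** With 84 values, Q3 is the mean of the 63rd and 64th ordered values. If at least 64 are 0 (64/84 = 76.2%), then Q1 = Q3 = 0 and the upper fence is 0 + 3 × 0 = 0. With fewer values available the limit is 61 of 80 or 58 of 76. Using illustrative non-zero scores cycling through 1 to 6, as on the LEI:

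| Zeros of 84 | Q3 | Non-zero values flagged |
|---|---|---|
| 50 (60%) | 3 | 0 of 34 |
| 54 (64%) | 2 | 0 of 30 |
| 59 (70%) | 1 | 8 of 25 |
| 62 (74%) | 1 | 6 of 22 |
| 63 (75%) | 0.5 | 13 of 21 |
| 64 (76%) | 0 | 20 of 20 |
| 67 (80%) | 0 | 17 of 17 |

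At exactly 75% zeros the collapse is not complete, because Q3 is the mean of 0 and the smallest positive value.

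**What is left.** After exclusion at 64 zeros, all 64 remaining values are 0. A negative binomial fit to such data failed with a singular matrix. For quantile regression, every percentile of an all-zero outcome is 0 in both arms, so any difference is 0 by construction and says nothing about treatment.

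**How likely.** The documents give no zero share for any score, so this is a range. If each patient scores 0 with probability p, the binomial chance of at least 64 zeros in 84 is:

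| p | Chance of full collapse |
|---|---|
| 0.60 | 0.001 |
| 0.65 | 0.02 |
| 0.70 | 0.13 |
| 0.75 | 0.46 |
| 0.80 | 0.84 |
| 0.85 | 0.99 |
| 0.90 | 1.00 |

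**Partial loss.** Trials of 84 patients were simulated with non-zero scores lognormal, median 40 and log-SD 0.8 (assumed):

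| Expected non-zero | Non-zero values flagged | Trials with all flagged |
|---|---|---|
| 10% | about 100% | about 100% |
| 20% | about 90% | about 84% |
| 25% | about 60% | about 46% |
| 40% | about 9% | close to none |

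**Primary endpoint.** For a normal variable with SD 1.57 and N = 84, about 0.003 values per trial are flagged. PASDAS is not touched by this mechanism.

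**The case against.** The reach is small. Flagged values stay in the main analysis, success is defined on PASDAS alone (SAP 11.1), and all five scores are secondary; they become exploratory if the primary comparison is not significant (SAP 11.2). Exclusion applies to data points in one sensitivity analysis, so no patient is lost from the trial. All of this stands and limits the point to a robustness check.

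The evidence that the data will be this sparse is also thin. The zero-median fallback in SAP 11.2 covers PASI and DLQI only and says nothing about LEI, LDI or mNAPSI. A zero median needs only about half the values at 0, well short of 76%; the steps beyond the 75th percentile are a contingency and do not report what was seen. For LDI, restricting to patients with dactylitis could lower the zero share considerably if it means dactylitis at baseline, although scores that resolve to 0 during follow-up would remain. A calculation over all 84 patients does not therefore describe the LDI analysis. These limits stand too, and are why the point is conditional.

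A reader might infer that a real effect would end up wrongly reported as resting on outliers. The documents and the calculations do not support that. In the extreme case the negative binomial model fails openly, and SAP 11.2 requires a substitute for a Table 11.2.1 model that does not converge to be highlighted as a deviation. Nothing here shows how often a model that does fit would give a misleadingly weakened effect. What the objection does not answer is that no substitute model can recover an effect from all-zero data.

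**Conclusion.** The point holds as a conditional defect in a secondary sensitivity analysis. As written, SAP 8.2 flags every non-zero value of a floor-at-0 score once more than three quarters of the values at a visit are 0 (64 or more of 84), and the exclusion analysis for that score and visit then cannot estimate a treatment effect. Near that share the loss is partial but sizeable; at 60 to 65% zeros it is small or nil in the examples above.

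This rests on three assumptions: quartiles pooled within visit; zero shares that the documents do not give; and, for the percentages of values lost, a lognormal shape for the non-zero scores. For LDI it also depends on how the dactylitis restriction is applied. It should be corrected because a robustness check that removes the residual disease under comparison is uninformative. It gives no reason to doubt the main analyses or the primary result.

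**What to change.** In SAP 8.2, apply the 3 × IQR exclusion analysis only to continuous interval outcomes with IQR above 0. For LEI, LDI, PASI, mNAPSI and DLQI, use the fence or simple range checks only to raise data-entry queries. Replace the exclusion analysis for these five by leave-one-out influence: refit the specified negative binomial or quantile model omitting one patient at a time, and report the smallest and largest treatment coefficient. State that quartiles are pooled over arms within visit, and state when a patient counts as having dactylitis for the LDI analysis.

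The cost is a paragraph of SAP text and a short loop in the analysis code. The sensitivity analysis will then differ by outcome type, which is a small loss of uniformity. SAP version 4.0 already post-dates unblinding, so the revision history and the trial report should label this as a post-unblinding change to a sensitivity analysis.
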